LIST OF ABBREVIATIONS AND RELEVANT DEFINITIONS

AE	Adverse Event
AR	Adverse Reaction
CA	Competent Authority
CCMO	Central Committee on Research Involving Human Subjects; in Dutch: Centrale Commissie Mensgebonden Onderzoek
DSMB	Data Safety Monitoring Board
EudraCT	European drug regulatory affairs Clinical Trials
GCP	Good Clinical Practice
IB	Investigator's Brochure
IMP	Investigational Medicinal Product
IMPD	Investigational Medicinal Product Dossier
METC	Medical research ethics committee (MREC); in Dutch: medisch ethische toetsing commissie (METC)
(S)AE	(Serious) Adverse Event
SPC	Summary of Product Characteristics (in Dutch: officiële productinfomatie IB1-tekst)
Sponsor	The sponsor is the party that commissions the organisation or performance of the research, for example a pharmaceutical company, academic hospital, scientific organisation or investigator. A party that provides funding for a study but does not commission it is not regarded as the sponsor, but referred to as a subsidising party.
SUSAR	Suspected Unexpected Serious Adverse Reaction
Wbp	Personal Data Protection Act (in Dutch: Wet Bescherming Persoonsgevens)
WMO	Medical Research Involving Human Subjects Act (in Dutch: Wet Medisch-wetenschappelijk Onderzoek met Mensen)

SUMMARY

Rationale: Cellulitis is among the most common infections leading to hospitalization, yet the optimal duration of therapy remains ill defined. Pragmatically Dutch guidelines advise 10 to 14 days of treatment with flucloxacillin, which is currently standard of care. Recently it has been shown that antibiotic treatment for pneumonia and urinary tract infections can safely and significantly be shortened. Importantly, in an outpatient setting, treatment of uncomplicated cellulitis with 5 days of antibiotics was as effective as 10 days. We hypothesize that there is no difference in outcomes when patients hospitalized with cellulitis are treated with either a short-course (6 days) or standard-course (12 days) of antibiotics.

Objective: To determine whether 6 days of flucloxacillin has equal efficacy compared to 12 days in patients hospitalized with cellulitis who after 5 days of initial therapy have substantially improved, defined as absence of fever (temp $> 38.0^{\circ}\text{C}$) and improvement in cellulitis severity score (self-reported or investigator-assessed).

Study design: Multicentre, randomized, double-blind, placebo-controlled non-inferiority trial.

Study population: Patients hospitalized for cellulitis, > 18 years of age.

Power calculation (non-inferiority design): a total sample size of 316 randomized patients gives 80% power to reject the null hypothesis of non-inferiority assuming a 15% failure rate, considering a difference of 10% as equivalence limit, with a 0.05 significance level.

Intervention: 6 days of flucloxacillin followed by another 6 days of flucloxacillin or placebo.

Main study parameters/endpoints: The primary endpoint is resolution of cellulitis at 14 days, defined as disappearance of warmth and tenderness at the site of infection, with substantial improvement in erythema and edema, and without recurrence by day 28, defined as the need of additional antibiotic therapy for cellulitis.

Secondary study endpoints include a test of cure with a different set of criteria for cure by day 14 and relapse by day 28, recurrence of cellulitis by day 90, speed of recovery as determined by improvement in cellulitis severity score and self assessment of subjective pain and swelling on VAS scales (0-10), Health-related Quality of Life (Dutch SF-36 questionnaire), and health care resource utilisation as determined by total antibiotic use and effect on direct and indirect health-care associated costs (economic evaluation and budget impact analysis).

Statistical analysis: Analysis will be based on intention-to-treat basis. Groups will be compared for the primary endpoint with Chi-squared test and Cochran-Mantel-Haenszel test for adjustment for the baseline covariates to evaluate the non-inferiority hypothesis. Secondary outcome parameters will be analyzed using Chi-squared test, two group t-test or Mann-Whitney test when appropriate.

Nature and extent of the burden and risks associated with participation: All study participants will have to complete a maximum of five sets of questionnaires (some by phone) and a maximum of five venous punctures. Potential risks include inferiority of 6 days of antibiotics compared to 12 days of treatment, i.e. a slower recovery of patients in the intervention group. Given the results of earlier trials on shortening of antibiotic therapy in pneumonia and urinary tract infections, we do not expect this to be the case. In our view the

small risk that 6 days will be inferior compared to 12 days offsets the profits which a shortening of antibiotic therapy for cellulitis potentially yields.

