3.3 Time schedule of study procedures for participants

	Day 0	Day 2-3	Day 5-6	Day 14-15	Day 28-29	Day 90
Informed consent	X					
In- and exclusion criteria	X					
Physical examination	X		X	X	X	
Laboratory measurements (usual care)	X					
Venous puncture	X	X	X	X	X	
Skin biopsy (see chapter 7)	X					
Clinical cellulitis score	X	X	X	X	X	
Self assessment score (0-10 scale)	X	X	X	X	X	X
SF-36 questionnaire & EQ-5D	X				X	X
Health care utilization questionnaire			X		X	X
Skin swabs (see chapter 7)	X			X		

Table 1. Time table of study procedures for participants

Up to day 28-29, patients will be evaluated face to face either in the clinic or at home. Self assessment scores and questionnaires to be performed on day 90 will be mailed to patients beforehand. On day 90, the investigators will review the answers and scores by telephone. Laboratory measurements collected through usual care will be collected when available. In exceptional cases, where inclusion would be hampered by people's willingness or ability to have so many follow-up visits, the decision can be made by the investigators to perform the day 28-29 visit solely by telephone. In this case the primary endpoint, questionnaires and medication information would be assessable. Physical examination, cellulitis severity score measurement and blood collection will not be possible.

The above table displays the ideal time schedule for participants. However, patients can be included until 72 hours after admission. When patients are included during 24-72 hours, the day 2-3 visit is skipped. The check for improvement on day 5-6 then also allows for self-reported improvement as marker for clinical improvement, due to the investigator not being present at the time when the disease was likely at its most severe. Self-reported improvement is also rated using the seven aspects of the cellulitis severity score; patients will be asked if they think that they have improved, taking all those aspects into account.

[figure not shown]

Figure 1. Flow diagram for study participants**3.4 Time schedule of the study**

Months 1-4:	Preparation of study and obtaining ethical approval
Months 5-44:	Enrolment of patients
Month 44:	Last patient enrolled
Month 47:	Last follow-up visit of last enrolled patient
Months 47-48:	Analysis of results

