4. STUDY POPULATION

4.1 Population

We plan to randomize 316 patients. All adult patients admitted to the hospital with cellulitis (see definition in appendix I) will be eligible for inclusion. The cohort comprises 316 subjects to be recruited by the Departments of Infectious Disease and Dermatology at the Academic Medical Center, the VU Medical Center and the University Medical Center Utrecht in collaboration with 8 affiliated teaching hospitals as mentioned above. These hospitals provide secondary and tertiary care to a large heavily populated urban region of the Netherlands. Participating hospitals have declared that they expect to admit at least 20 suitable cellulitis patients yearly. Assuming that 75% of patients will partake in this study, this brings the estimated recruiting period to approximately 3.5 years (396 patients / (8 centers * 15 patients yearly) = 3.3 years → this number has been adjusted to 316 as of July 2015, which puts the estimated deadline at April 2017). A dedicated research nurse will help with patient enrolment.

If during the enrolment process it is expected that the recruiting period will last longer than 3.5 years, additional hospitals will be approached to participate in the study. The number of inclusions will be evaluated on at least a yearly basis.

As control group for the microbiota analysis from the skin swabs (see 7.3.6), we will include 20 healthy volunteers who are age- and gender-matched to the population of whom the skin swabs are analysed. Eligible volunteers are aged 18 or older, and should not have had cellulitis, abscesses, dermatitis, or psoriasis in their leg in the past 3 months. The rest of the protocol is not applicable to these volunteers, except when specifically mentioned. These patients will have completed their participation in this study, as soon as the skin swab has been taken.

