4.4 Sample size calculation

The sample size calculation of is based on three large randomised clinical trials which were published in high impact journals in 2014. From the DISCOVER, ESTABLISH and SOLO trials, information was gathered on cellulitis clinical cure rates as assessed by investigators after therapy:

DISCOVER²¹ (dalbavancin vs vancomycin-linezolid): (information from supplementary data)

- Clinical status evaluation at the end of therapy (day 14) of cellulitis patients:
 - o Cured: 297/324 and 276/301

ESTABLISH²⁷ (tedizolid vs linezolid): (information received from authors via e-mail)

- Investigator assessed response at post-therapy evaluation (7-14 days after end of therapy) of cellulitis patients:
 - o Cured: 265/301 and 263/307

SOLO²⁸ (oritavancin vs vancomycin): (information received from authors via e-mail)

- Investigator assessed clinical cure rates at the post-therapy evaluation (7-10 days after end of therapy) of cellulitis patients:
 - o Cured: 294/387 and 315/400

Total cure rates:

- $$(297+276+265+263+294+315) / (324+301+301+307+387+400) = 1710 / 2020 = 84,65\% \text{ cure rate}$$

A two-group large-sample normal approximation test of proportions with a one-sided 0.050 significance level will have 80% power to reject the null-hypothesis, assuming a success rate

of 85% and considering a difference of 10% between the two groups as equivalence limit, if the sample size of each group is 158. This gives a total sample size of 316 patients.

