7.5 Replacement of individual subjects after withdrawal

Not applicable, an intention-to-treat analysis will be performed.

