9. STATISTICAL ANALYSIS

9.1 General considerations

For the modified intention to treat analysis, all randomized patients who received at least one dose of study medication will be included. Missing data will be handled with multiple imputation, due to its nature of giving standard errors and P values that incorporate missing-data uncertainty²².

For the per protocol analyses, only randomized patients whose compliance was clear, and who received at least four days of trial medication (in clinical successes), or one day of trial medication (in clinical failures) will be included.

For the per protocol analysis of our primary outcome, patients are considered clinically cured if there is resolution of cellulitis at 14 days defined as disappearance of warmth and tenderness at the site of infection, with substantial improvement in erythema and edema, and without recurrence by day 28, defined as the need of additional antibiotic therapy for cellulitis. Clinical failure is defined as the persistence or progression of signs and symptoms of the acute process after randomization, or the inability to complete the study owing to adverse events. The response is deemed indeterminate when the patient (i) received less than 80% of the study drug for reasons other than clinical failure, (ii) acquired a concomitant infection outside of the skin requiring antibiotic treatment, (iii) was lost to follow-up, or (iv) died unrelated to the primary diagnosis.

For the per protocol analysis of our first secondary outcome (paragraph 7.1.2), patients are considered clinically cured if there is resolution of cellulitis at 14 days, defined as the absence of fever and an improvement of the combined symptom score of warmth, tenderness, erythema and edema by 2 or more points since patient inclusion (or it has reached 0), and without recurrence by day 28, defined as a stable or further improved combined symptom score, absence of fever and no need of additional antibiotic therapy for cellulitis. The response is deemed indeterminate when the patient (i) received less than 80% of the study drug for reasons other than unblinding / requiring new antibiotics for cellulitis / being unable to continue due to adverse effects, (ii) acquired a concomitant infection outside of the skin requiring antibiotic treatment, (iii) was lost to follow-up, or (iv) died unrelated to the primary diagnosis. Those whose outcomes are not cured or indeterminate are considered clinical failures.

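### Does randomising exactly the 316 patients that the formula requires leave the trial short of its stated 80% power?

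*Combined protocol and SAP*

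**What the plan says.** Section 4.4 takes a pooled cure rate of 1710/2020 = 84.65% from three published trials and rounds it to 85%. It then specifies a one-sided 0.05 test with 80% power, "considering a difference of 10% between the two groups as equivalence limit, if the sample size of each group is 158", and doubles that to 316. Section 4.1 carries the same number into recruitment: "We plan to randomize 316 patients". The Summary attaches the 80% to patients randomised: "a total sample size of 316 randomized patients gives 80% power to reject the null hypothesis of non-inferiority assuming a 15% failure rate". No attrition or non-evaluable rate is stated.

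The plan does provide for losses. On replacing withdrawn patients, section 7.5 reads "Not applicable, an intention-to-treat analysis will be performed". In section 9.1 the modified intention-to-treat set is defined so that "all randomized patients who received at least one dose of study medication will be included", which leaves out undosed patients, and "Missing data will be handled with multiple imputation". Section 9.3 tests non-inferiority with a one-sided 95% limit on the absolute risk difference.

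The plan also works to keep losses low. Section 5.5 makes home visits the main follow-up route. Section 3.3 allows the day 28-29 visit by telephone in exceptional cases and adds: "In this case the primary endpoint, questionnaires and medication information would be assessable". Section 11.1 has antibiotic use after discharge taken from the patient and checked with the pharmacy if in doubt. Section 7.2 undoes a provisional weekend randomisation when the patient turns out not to qualify.

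**The concern.** A sample size formula counts patients whose outcome is known, while the Summary and section 4.1 count patients randomised. Using one number for both is safe only if nearly every randomised patient yields an informative primary outcome. Here the formula gives 157.66 per arm, so rounding up to 158 is the only slack.

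Some loss is foreseeable. Patients may withdraw and are not replaced, undosed patients leave the analysis set, and the endpoint needs a skin examination at day 14-15 for which section 3.3 offers no telephone substitute. Multiple imputation keeps a dosed patient in the analysis but does not in general restore the information in a missing outcome.

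In addition, the 85% is rounded up from 84.65% and comes from cure rates measured at differing times. One of them is described as "Clinical status evaluation at the end of therapy (day 14) of cellulitis patients", whereas this trial's endpoint combines day 14-15 resolution with no recurrence by day 28-29.

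What is at stake is power. If the short course is truly as good as the long one, lost outcomes raise the chance that the confidence limit crosses the margin and the trial ends without an answer.

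**Working it through.** **Inputs.** Success 85% in both arms, margin 0.10, one-sided alpha 0.05, power 80% and 158 per arm (all section 4.4); 316 randomised (section 4.1, Summary); one-sided 95% limit on the risk difference (section 9.3). The documents give no loss rate, so the rates below are assumptions.

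**1. Reproduce the plan's figure.**

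n per arm = (1.645 + 0.842)² × 2 × 0.85 × 0.15 / 0.10² = 157.66 (unrounded z values), rounded up to 158; 2 × 158 = 316.

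Power = Φ(0.10 / √(2 × 0.85 × 0.15 / 158) − 1.645) = Φ(2.489 − 1.645) = 80.1%.

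The stated 316 and 80% both follow. The Summary omits that the 0.05 is one-sided, but section 4.4 says so.

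**2. Does a small loss break the 80%?** By the normal approximation, one lost outcome (157.5 per arm on average) gives 79.97%, just under 80%. That is finer than the approximation can support. Summing exact binomial probabilities at 85% success, with an unpooled Wald limit (assumed, since section 9.3 names no formula), gives:

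| Informative outcomes | Lost of 316 | Exact power |
|---|---|---|
| 158 vs 158 | 0 | 80.3% |
| 158 vs 157 | 1 | 80.1% |
| 157 vs 157 | 2 | 79.7% |
| 156 vs 156 | 4 | 79.9% |
| 155 vs 155 | 6 (1.9%) | 79.6% |

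The sequence is not monotone (two lost scores below four lost) because counts are discrete. Every row rounds to 80%.

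**3. Rounding 84.65% to 85%.** At 84.65% the formula asks for 160.64, that is 161 per arm. Power at 158 is 79.4% by the approximation and 79.7% by exact enumeration. The effect is a fraction of a point, and section 4.4 shows the rounding openly.

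**4. Larger losses.** With a share L of outcomes lost and nothing recovered by imputation, n = 158 × (1 − L):

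- L = 5%: n = 150.1, power Φ(2.426 − 1.645) = 78.3%
- L = 10%: n = 142.2, power Φ(2.361 − 1.645) = 76.3%

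If imputation recovered half the information (also an assumption), n = 158 × (1 − L/2), and power would be 79.2% at 5% loss and 78.3% at 10%.

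**5. What counts as lost.** Home visits reach the day 14-15 examination as well as day 28-29. The endpoint is a composite, so a patient known to have needed further antibiotics for cellulitis by day 28-29 is a failure even if the day 14-15 examination was missed. The outcomes truly lost are those of undosed patients, and of dosed patients with no antibiotic need recorded whose day 14-15 findings or day 28-29 status are unknown.

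**The case for a change.** The best case for a change is that the Summary's sentence is about patients randomised, and a reader of the Summary alone would not learn that 80% presumes almost complete outcomes. The plan chooses multiple imputation because its standard errors carry the uncertainty from missing data. By the plan's own reasoning, then, missing outcomes widen the interval that decides non-inferiority. Undosed patients are outside the analysis set and imputation cannot bring them back. One added sentence would cost almost nothing.

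Most of this stands as description. No allowance is stated, and imputation does not make attrition free. It does not show that a figure in the plan is wrong. The 80% follows from the stated assumptions, and no passage gives an expected loss that the design then fails to meet. Falls of two points or more appear only at loss rates brought in from outside the documents. The added sentence would leave the number of patients, the margin, the analysis and the decision rule untouched.

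The mismatch between the source cure rates and this trial's composite endpoint is real, but its direction is unknown, so it cannot be used to say that 316 is too few.

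**Conclusion.** No change is needed. The sample size calculation is right, and its 80% holds to the nearest percentage point for losses up to about 2% of patients (six of 316). If 5% or 10% of outcomes were lost with nothing recovered, power would be about 78% or 76%. With equal true success of 85%, the chance of an inconclusive result would go from about 20% to about 22% or 24%. Those two rates are assumptions.

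Randomising the formula's number, with home-based follow-up, a telephone fallback for the later visit and imputation in place of replacement, is a fair trade-off in a trial with 90 days of follow-up per patient and a primary endpoint settled by day 28-29. A smaller number of informative outcomes costs power. It does not relax the 10-point criterion or alter how the result is read, since the interval at analysis shows the precision actually achieved. The missing allowance is an unstated detail that readers can supply for themselves.

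This rests on 85% success in both arms, an unpooled Wald limit for the exact figures, and loss that is spread about equally over the arms.

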7.1.2 Secondary study endpoints

- Resolution of cellulitis at 14-15 days, defined as the absence of fever and an improvement of the combined symptom score of warmth, tenderness, erythema and edema by 2 or more points since patient inclusion (or it has reached 0), and without recurrence by day 28-29, defined as a stable or further improved combined symptom score, absence of fever and no need of additional antibiotic therapy for cellulitis.
 - A per protocol analysis of this endpoint (see paragraph 9.1).
 - Sensitivity analyses with two modifications to the day 28 criteria:
 - Resolution of cellulitis at 14 days, defined as the absence of fever and an improvement of the combined symptom score of warmth, tenderness, erythema and edema by 2 or more points since patient inclusion (or it has reached 0), and with further improvement of the combined symptom score of 1 or more point(s) (or it has reached 0), absence of fever, and no need of additional antibiotic therapy for cellulitis by day 28
 - Resolution of cellulitis at 14 days, defined as the absence of fever and an improvement of the combined symptom score of warmth, tenderness, erythema and edema by 2 or more points since patient inclusion (or it has reached 0), and with further improvement of the combined symptom score of 2 or more point(s) (or it has reached 0), absence of fever, and no need of additional antibiotic therapy for cellulitis by day 28
- Recurrence of cellulitis by day 90 after inclusion, defined as the need of additional antibiotic therapy for cellulitis
- Speed of recovery, as determined by improvement in cellulitis severity score, and self assessment of subjective pain and swelling on Visual Analog Scales scales (0-10), assessed at baseline (day 0), days 2-3, 5-6, 14-15, 28-29 and 90 (day 90 self-assessment only)¹²
- Mean health-related Quality of Life (using the Dutch SF-36 questionnaire and the EQ-5D) at day 0, 28-29 and 90.

- Health care resource utilisation, as determined by total antibiotic use and effect on direct and indirect health-care associated costs

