9.3 Primary study parameter(s)

For the primary outcome, the proportion of successful treatments will be calculated for the two groups, and the absolute risk difference (with one sided 95% confidence limit) will be estimated to evaluate the non-inferiority hypothesis. In a secondary analysis, the difference in proportion in the two groups will be adjusted for relevant baseline covariates, using a logistic regression analysis. The difference in proportion of successful treatments will be estimated at mean values for the covariates.

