9.4 Secondary study parameter(s)

Differences in secondary outcome parameters will be reported as relative risk or mean difference (with 95% confidence interval), and p-values for statistical significance estimated with the Chi-square test, t-test or Mann-Whitney test, where appropriate. A Kaplan-Meier analysis will be performed to compare the time to relapse (defined as requiring additional antibiotics for cellulitis) between the two groups.

Variable/outcome	Hypothesis	Outcome measure	Methods of analysis
1. Primary			
Resolution without relapse	Intervention not inferior to control	Percent cured on day 14 without relapse by day 28 [binary]	Absolute risk difference
2. Secondary			
Resolution without relapse (per definition of protocol version 9.4, see paragraph 7.1.2, including both sensitivity analysis and per protocol analysis)	Intervention not inferior to control	Percent cured on day 14 without relapse by day 28 [binary]	Absolute risk difference (Per protocol analysis: χ^2 → Relative Risk)
Relapse by day 90	No difference	Percent with relapse [binary]	χ^2 → Relative Risk
Time to relapse	No difference	Relapse after cure [time to event]	Kaplan-Meier survival analysis
Objective speed of recovery	No difference	Cellulitis severity score [continuous]	Student's T-test or Mann-Whitney U test
Subjective speed of recovery	No difference	Visual analogue scales of pain and swelling [continuous]	Student's T-test or Mann-Whitney U test
Quality of life	No difference	SF-36 questionnaire score at day 0 and 90 compared to population, day 14 and 28 compared to day 5-6 [continuous]	Student's T-test or Mann-Whitney U test
Antibiotic usage	No difference	Total costs of antibiotic use [continuous]	Student's T-test or Mann-Whitney U test
Health care utilization	No difference	Total treatment associated costs, Health Care Utilization Questionnaire [continuous]	Student's T-test or Mann-Whitney U test
3. Subgroup analyses			
Cellulitis severity score on a continuous scale	Severity score affects rate of cure		Regression analysis, with interaction term for severity score
Diabetes mellitus vs no diabetes mellitus	Diabetes affects rate of cure		Regression analysis, with interaction term for (no) diabetes
4. Sensitivity analyses	Intervention not inferior to	All outcomes	

	control		
Per protocol analysis			Chi ² → Relative Risk
Primary outcome adjusted for baseline covariates			Cochran-Mantel-Haenszel → Relative Risk

Table 3. Analysis methods per outcome measures or variables

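### The Summary's primary test and Table 3's adjusted and per-protocol non-inferiority analyses use zero-difference tests or relative risks that do not address the 10-point margin set in 4.4

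*Combined protocol and SAP*

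**What the plan says.** **Design (4.4).** One-sided 0.05 level, 80% power, 85% success in both groups, and a limit of 10% on the difference between groups, giving 158 per group.

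**Main primary analysis (9.3).** "the absolute risk difference (with one sided 95% confidence limit) will be estimated to evaluate the non-inferiority hypothesis". The primary row of Table 3 also names the absolute risk difference. Section 9.3 does not restate the 10-point margin.

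**Summary, Statistical analysis.** Groups are to be compared "for the primary endpoint with Chi-squared test and Cochran-Mantel-Haenszel test for adjustment for the baseline covariates to evaluate the non-inferiority hypothesis".

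**Adjusted primary analysis, stated twice.**
- In 9.3, "the difference in proportion in the two groups will be adjusted for relevant baseline covariates, using a logistic regression analysis", and then "The difference in proportion of successful treatments will be estimated at mean values for the covariates". No confidence limit is named for this estimate.
- In the sensitivity block of Table 3, the row "Primary outcome adjusted for baseline covariates" has Cochran-Mantel-Haenszel as method and relative risk as output.

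**Per-protocol analyses.** Section 7.1.2 lists, under the first secondary endpoint, "A per protocol analysis of this endpoint (see paragraph 9.1"). In Table 3 that endpoint carries the non-inferiority hypothesis; its method cell begins "Absolute risk difference (Per protocol analysis" and continues with chi-squared and relative risk. Section 9.1 also defines a per-protocol analysis of the primary outcome. The only method listed for that one is the general per-protocol entry in the sensitivity block, again chi-squared with relative risk.

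**Reporting rule (9.4).** "Differences in secondary outcome parameters will be reported as relative risk or mean difference (with 95% confidence interval"), with p-values from the chi-squared, t or Mann-Whitney test. No margin on the relative-risk scale appears anywhere.

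**The concern.** A chi-squared or Cochran-Mantel-Haenszel test, as ordinarily run, tests a difference of zero and contains no margin. A non-significant result does not show that a 10-point loss has been excluded, and a significant one does not show that it has not. A relative risk can be set against 10 points only once a control cure rate is fixed, and the plan fixes none for that purpose.

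Table 3 lists the per-protocol and adjusted analyses as sensitivity analyses, and nothing in the plan makes the non-inferiority conclusion depend on them. Their purpose is to show whether the 9.3 conclusion holds up under other reasonable choices. As specified, they answer a different question. The adjusted primary analysis can in addition be run by two methods on two scales, which leaves a choice open after the data are seen. The Summary, read alone, describes a primary test that would not evaluate non-inferiority.

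**Working it through.** **1. The plan's own figure.** From 4.4: success 0.85 in both groups, margin 0.10, one-sided 0.05 (z = 1.645), 80% power (z = 0.842).

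n per group = (1.645 + 0.842)² × 2 × 0.85 × 0.15 / 0.10² = 157.7, rounded up to 158, or 316 in total.

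This matches the plan and confirms that the design is on the absolute-difference scale at a one-sided 5% level. Section 9.3 agrees with it.

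**2. Formulas.** With success proportions p₆ and p₁₂ and n per arm:
- risk difference d = p₆ − p₁₂; one-sided 95% lower limit = d − 1.645 × √[p₆(1−p₆)/n + p₁₂(1−p₁₂)/n];
- uncorrected chi-squared p-value;
- relative risk p₆/p₁₂ with a 95% interval on the log scale.

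Section 9.3 does not name an interval method; the Wald limit is used here.

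**3. The same data read both ways (illustrative counts).**

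| 6-day v 12-day | d (points) | lower limit (points) | excludes a 10-point loss? | chi-squared p | relative risk (95% CI) |
|---|---|---|---|---|---|
| 131/158 v 134/158 | -1.9 | -8.7 | yes | 0.65 | 0.978 (0.887 to 1.077) |
| 118/142 v 124/142 | -4.2 | -11.1 | no | 0.32 | 0.952 (0.864 to 1.049) |
| 121/158 v 134/158 | -8.2 | -15.5 | no | 0.064 | 0.903 (0.810 to 1.007) |
| 147/158 v 156/158 | -5.7 | -9.3 | yes | 0.011 | 0.942 (0.900 to 0.987) |

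Row 2 is row 1 after an assumed 16 per-protocol exclusions per arm. Row 4 shows the reverse mismatch: the margin is met although the test is significant.

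**4. If the Summary's test were taken at its word.** Suppose a non-significant two-sided 5% chi-squared test, or a better short-course result, were read as non-inferior. Exact binomial enumeration at 158 per arm with true success 85% v 75%, exactly at the margin, gives a declaration of non-inferiority in 39.5% of trials. The 9.3 rule gives 5.2%.

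**5. A relative risk cannot stand in for the margin.** The relative risk equal to a 10-point loss is 1 − 0.10/p₁₂. At the pooled cure rates of the three trials in 4.4:
- SOLO, 609/787 = 77.4%: 0.871
- ESTABLISH, 528/608 = 86.8%: 0.885
- DISCOVER, 573/625 = 91.7%: 0.891

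No single relative-risk limit reproduces 10 points across these rates.

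**6. How often a supporting analysis would need to speak up.** Simulated trials had 158 per arm and 12-day success 85%, with per-protocol loss **assumed** independent of outcome. Section 9.1 in fact sets different minimum days of medication for successes and failures, so this is a simplification. Among trials that pass 9.3, the share whose per-protocol lower limit does not clear -10 points:

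| True 6-day success | 5% loss | 10% loss | 20% loss |
|---|---|---|---|
| 85% | 4.5% | 7.5% | 13.3% |
| 82% | 8.8% | 13.7% | 22.1% |
| 80% | 11.7% | 17.7% | 27.3% |

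In every cell, at least 99.7% of these discordant trials have a non-significant per-protocol chi-squared test.

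**7. Stratified check (illustrative diabetes strata).** 28/40 v 30/40 and 93/118 v 104/118 give Cochran-Mantel-Haenszel p=0.063 and Mantel-Haenszel relative risk 0.903 (0.811 to 1.006). The same strata give a Mantel-Haenszel risk difference of -8.2 points with lower limit -15.4. The weighting can stay; only the scale has to change.

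**The case against.** **The primary test is complete without these rows.** This stands. Section 9.3 with the margin in 4.4 fully specifies the unadjusted primary analysis, so the point concerns consistency and supporting analyses.

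**The per-protocol risk difference can be computed from the same 2×2 table.** True, but it would then be an unplanned calculation. The fault is that the margin comparison is not specified for these rows, not that it is unobtainable. Raw totals do not give the adjusted estimate.

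**The rates in step 6 measure patient loss, not the choice of test.** This also stands. The discordance would occur equally after the fix, which only makes it visible. Non-significance is nearly automatic in trials that have already passed 9.3. Section 5.4 expects no adherence problem, so the loss may be small. The rates describe when a margin-based supporting analysis would be informative; they are not an error rate of the plan.

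**The per-protocol example is selected.** Going from row 1 to row 2 removes 3 of 27 failures from the 6-day arm but 6 of 24 from the 12-day arm, which fits poorly with a rule that keeps failures after one day of medication. Near-proportional exclusion, 118/142 v 120/142, gives a limit of -8.6. With 16 random exclusions per arm, a limit at or below -10 arises in about 30% of draws, and one at least as low as row 2 in about 8%. The example shows what can happen, not what is likely.

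**The sensitivity block is hard to read.** Its hypothesis cell is split by a page break and its outcome cell covers all outcomes, so the chi-squared entry may be shorthand. The primary-outcome per-protocol reading is therefore less certain. The first secondary row is explicit.

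**The adjusted estimate may inherit the limit named just before it in 9.3.** Plausible, but Table 3 still gives another method and scale.

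**Conclusion.** The concern holds and should be fixed. Three places in the current text conflict with the sound specification in 9.3: the Summary's primary test, Table 3's adjusted primary analysis, and Table 3's per-protocol analysis of the first secondary endpoint. The same conflict probably extends to the primary outcome's per-protocol analysis, with less certainty. Followed as written, these analyses yield a zero-difference p-value or a relative risk, and neither says whether a 10-point loss is excluded. Step 3 shows disagreement in both directions.

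The main 9.3 analysis, its type I error and the 316-patient sample size are not affected. The 39.5% figure applies only if a non-significant chi-squared test were read as non-inferiority. The step 6 rates rest on the assumed per-protocol loss.

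**What to change.** - **Summary:** replace the chi-squared and Cochran-Mantel-Haenszel wording with the 9.3 analysis: 6-day minus 12-day success, one-sided 95% lower limit, compared with -10 points.
- **Per protocol:** use that same measure and limit for the primary outcome and, in place of chi-squared and relative risk, for the first secondary endpoint. State whether the 10-point margin applies to the latter, since 4.4 sets it only for the primary sample size.
- **Adjusted primary analysis:** choose one method that returns a risk difference with a lower limit, and make 9.3 and Table 3 agree. Either 9.3's logistic method or a Mantel-Haenszel stratified risk difference would serve. If the randomisation strata (diabetes and site, section 7.2) are used, check first that the diabetes-by-site cells are not too sparse.
- **Table 3 sensitivity block:** limit chi-squared with relative risk to binary outcomes whose hypothesis is no difference.

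Cost: one Summary sentence, one clause in 9.3 and three Table 3 entries. No new data, no extra patients and no change in sample size.
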